#### 15.6.6 MISSED BASE APPOINTMENT SCRIPTS AND PROCEDURE

If a participant misses a baseline appointment and is unresponsive to three contact attempts (mix of voice mail and SMS messages) sent in intervals of 2 days between messages, then mark the participant as “inactive” and move to enroll another candidate.

If another candidate is identified and attends the baseline appointment, then mark the inactive candidate as “replaced” in the participant database.

---

**15.6.6.1 VOICEMAIL SCRIPT: MISSED BASELINE APPOINTMENT**

*Hi, this is [YOUR NAME] from GogyUp. I'm calling to leave a message for [NAME OF PARTICIPANT].*

*[NAME OF PARTICIPANT], please call or text me when you have a moment at [[contact]](#)*

*J. That's [name]*

Record each contact attempt and outcome in the comments area of the participant's database record.

---

**15.6.6.2 SMS SCRIPT: MISSED BASELINE APPOINTMENT**

*Hi [ NAME OF PARTICIPANT ]! This is [ YOUR NAME ] from GogyUp. We were going to meet [ TIME AND DAY OF MEETING ]. When would be a good day and time to reschedule?*

Record each contact attempt and outcome in the comments area of the participant's database record.

## 15.6.7 INTERVENTION GROUP – ONBOARDING FOR GOGYUP READER

After the baseline assessment is completed, display the quick start guide (see section 15.7.2) and ask if the participant is ready to try GogyUp Reader.

If the participant does not have the time or access to an internet-connected device, explain that they will receive a quick start guide with their network access reimbursement. If they would like help with accessing the app, they are always welcomed to contact the research coordinators.

If the participant is ready and available, walk through these steps.

- 1) Point to step 1 in the Quick Start Guide and point out that the GogyUp Reader can be used on any Android or iOS device – or on a PC with a Chrome or Edge web browser.
- 2) Ask the participant which device they plan to use and verify they are able to find the GogyUp Reader on their device's app store (or through their browser).
- 3) Point to step 2 and state that the next step is to fill out a GogyUp profile. This information is used to sync progress so that if they want to use GogyUp on another device, they can.
  - a. Note that they don't have to use their real name.
  - b. For the **UserName** they should use their assigned **Study Number**.
- 4) Point to step 3 in the Guide and note that if the participant has a preferred language other than english, they may select from the options to have an individual word translated into that preferred language.
- 5) Point to step 4 and emphasize that the participant should put in “**ninr1**” in the invite code box – this is needed so that the participant has access to the content library for the study.
- 6) Guide the participant to tap “Save profile” and then point out the different features in the app:
  - a. **Points A&B** in the Guide's Features section: Touch any word to launch the “word menu”
    - i. Request that the word be spoken, defined, or translated.
    - ii. Point out the “hear sentence” button if the participant wants the entire sentence spoken.
    - iii. Note that some words will have a “practice” button – this is a quick, optional spelling activity and isn't related to the study.
  - b. **Point C:** Demonstrate how the EZText button can instantly re-format the text so that it fits better on smaller screens and enables individuals to focus on individual words and phrases. Point out how the participant can increase the font size.
- 7) Point out how to close the “x” in the upper right to go back out to the page where the participant can access the help menu and get technical support.

#### 15.7 STEP 7: PROVISION PARTICIPANT

Following completion of the baseline assessment, provisioning participants will be dependent on the group each is enrolled in.

Depending on the participant's assignment, send one of the following via postal mail:

- **Control Group:** the set of education materials and welcome letter.
- **Intervention Group - Network Access:** the \$25 gift card to cover their network expense and instructions for downloading and signing-in to the GogyUp Reader app.
- **Intervention Group - Tablet:** If the participant requested a tablet, instructions for powering on the tablet and accessing the materials in the GogyUp Reader app. Accessing GogyUp on the tablet will be a “one click” experience – the GogyUp app and GogyUp account required to access the materials will be pre-provisioned with the end-user’s information.

Depending on IRB guidance, each participant's provider will also be sent an enrollment notification via postal mail.

RCT of Assistive-Reading Technology for Post-Visit Type 2 Diabetes Patient Education

Version 1.4

Protocol 1

10 February 2023

15.7.1 INTERVENTION GROUP – WELCOME LETTER

Removing barriers to understanding.

Street Address 1

Street Address 2

City, State Zip

[ DATE ]

Welcome to the study!

In this envelope, please find:

- the \$25 gift card to help cover network costs
- “How to Use GogyUp Reader” quick start guide.

Please remember to use GogyUp Reader a few days each week to review information about diabetes.

If you need help with GogyUp Reader or have questions about the study, contact our research coordinator:

- Phone / Text: [contact]
- eMail: [[contact]](mailto:[contact])

You can also review study information here: [gogyup.com/study](http://gogyup.com/study)

Your follow-up assessment is scheduled for **{followupAssessmentDate}** at **{followupAssessmentTime}**. If you need to change it, please call the research coordinator: [contact]

Remember, the information in GogyUp Reader does not replace the information you receive from your doctor or clinic. **If you have questions about diabetes or your health, contact your doctor or clinic.**

Sincerely,  
The GogyUp Study Team

encl.

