### 5.3 JUSTIFICATION FOR INTERVENTION

Intervention delivery via mobile software app is precisely central to the potential benefit of the intervention: in-the-moment support for patients' capacity to interact with complex written patient materials. We will only have two actual study contacts beyond recruitment and pre-screen/consenting: baseline and follow-up at three months, which will only include obtaining outcome measurement administration necessary to analyze data to meet our study objectives. We will have app usage data (internal to GogyUp) that can provide any indication as to whether lack of differences between arms in an intent-to-treat analysis is simply due to low app usage (this would provide a finding, and inform future study design, rather than being a failure).

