7	
Provisioning
 
RC will enroll the participant in the assigned group.
 
An administrative assistant will send out:
 
  
 Intervention	Control	
   
  
 
• Directions for downloading the mobile app or accessing the webapp.
 
• Directions for creating a GogyUp account and signing into the study’s walled library.
 
• Enrollment Notice to Provider
 
 	 
 
• Packet of reading materials sent weekly
 
• Enrollment Notice to Provider
 
 	
  
 
RC will be provided daily activity reports by the administrative assistant. If a participant’s account has no activity at the start of the study period, the RC will contact the participant to ensure they have access to GogyUp and are able to log in.
	Intervention	Control	
 
• Directions for downloading the mobile app or accessing the webapp.
 
• Directions for creating a GogyUp account and signing into the study’s walled library.
 
• Enrollment Notice to Provider
 
	
 
• Packet of reading materials sent weekly
 
• Enrollment Notice to Provider
 
	
Scripts:
 
 
• Shipment Notification SMS / eMail
 
• Enrollment Notice to Provider
 

Intervention	Control					

 
• Directions for downloading the mobile app or accessing the webapp.
 
• Directions for creating a GogyUp account and signing into the study’s walled library.
 
• Enrollment Notice to Provider
 
	
 
• Packet of reading materials sent weekly
 
• Enrollment Notice to Provider
 
					

Step	Description	Documents & Scripts

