#### 15.7.4 CONTROL GROUP – WELCOME LETTER

Use the following letter template to mail the hardcopy reading materials to study participants in the control group.

Street Address 1

Street Address 2

City, State Zip

[ DATE ]

Welcome to the study!

Here are your diabetes reading materials! Please feel free to review them over the next 12 weeks.

If you have questions about the study, contact our research coordinator:

- Phone / Text: [contact]
- eMail: [[contact]](mailto:[contact]).

You can also review study information here: [gogyup.com/study](http://gogyup.com/study)

Your follow-up assessment is scheduled for **{followupAssessmentDate}** at **{followupAssessmentTime}**. If you need to change it, please call the research coordinator: [contact]

Remember, the information in GogyUp Reader does not replace the information you receive from your doctor or clinic. **If you have questions about diabetes or your health, contact your doctor or clinic.**

Sincerely,  
The GogyUp Study Team

encl.

---

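### The two welcome letters prompt reading unequally (a weekly frequency for the app arm, an open invitation for control), so part of any arm difference could reflect the prompt rather than assistive reading

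*Combined protocol and SAP*

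**What the plan says.** The app-arm letter (15.7.1) sets a frequency: "Please remember to use GogyUp Reader a few days each week to review information about diabetes". The control letter (15.7.4) gives permission without a frequency: "Please feel free to review them over the next 12 weeks". It then closes with a sentence that names the app to people who do not have it: "Remember, the information in GogyUp Reader does not replace the information you receive from your doctor or clinic".

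Step 7 of the workflow table (11.1.4) adds monitoring and a contact that apply to app accounts only. It says "RC will be provided daily activity reports by the administrative assistant", and where an "account has no activity at the start of the study period, the RC will contact the participant to ensure they have access to GogyUp" and can log in. The control cell of the same step reads "Packet of reading materials sent weekly", whereas sections 15.7 and 15.7.4 describe one set of materials sent with one letter.

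The body of the protocol frames the comparison differently. Section 5.1.3 compares the app used with written materials against those same materials alone. Section 2.1 leaves it to users whether and when to open the app. Section 7.1.2 requires no level of use and notes that control-arm activity cannot be measured. Section 5.3 says "We will only have two actual study contacts beyond recruitment and pre-screen/consenting", meaning the baseline and three-month assessments.

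**The concern.** The trial aims to learn whether assistive reading improves health literacy. If one arm is asked to read several days a week and the other is told it may read if it wishes, the arms differ in two respects: the technology and the prompt. Reading more of the same fact sheets could by itself move self-reported answers about understanding health information or having enough of it, whatever the medium. Randomisation does not remove this difference, because it is introduced after assignment.

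The result is meant to inform a fully powered Phase II trial (3.1, 3.2), so a misattributed effect would carry forward into that design. The prompt also affects a second planned use of the data. Section 5.3 intends to read low app use as a finding about uptake, but use after a request to log on several days a week is not purely self-directed use.

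**Working it through.** **1. What each arm receives in the supplied text**

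- Frequency wording in the welcome letter: a few days per week for the app arm (15.7.1); none for control (15.7.4).
- Assignment and baseline scripts: no reading frequency for either arm (15.5.1.2, 15.5.1.3, 15.6.4, 15.6.5, 15.6.7). The letter is thus the only place found that sets one.
- Staff contact after baseline: an access and log-in contact for app accounts silent at the start (11.1.4, Step 7). No counterpart for control was found.
- Mailings to control: one set (15.7, 15.7.4) or weekly packets (11.1.4, Step 7). Over the 12 weeks in the control letter, that is 1 mailing or up to 12.

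**2. Whether the analysis can separate prompt from app**

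The ANCOVA adjusts for the baseline score (10.4.2). The adherence analysis is exploratory and uses app sessions and time (10.4.9). Control reading is unmeasured (7.1.2). None of these can divide the arm difference into a prompting part and an app part.

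**3. Reproducing the plan's power (10.2)**

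Inputs: SD 0.74 for the Understanding subscale (10.2); two-sided 5% level (10.4.1). SE = SD × √(2/n); power ≈ Φ(difference/SE − 1.96).

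- n = 60 per arm: SE = 0.74 × √(2/60) = 0.135. For 0.37: Φ(2.739 − 1.96) = 78.2%, against 78% stated.
- n = 80 per arm: SE = 0.74 × √(2/80) = 0.117. For 0.30: Φ(2.564 − 1.96) = 72.7%, against 73% stated.

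The power figures are sound. They take the whole arm difference as the app's effect.

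**4. Illustration of the stake**

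Suppose the app does nothing and the prompt shifts the mean by b. The value of b is an assumption; the documents give none. The chance of a significant result is P(|Z + b/SE| > 1.96). At 80 per arm:

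- b = 0: 5.0%.
- b = 0.05: b/SE = 0.427; P(Z > 1.533) + P(Z < −2.387) = 0.063 + 0.008 = 7.1%.
- b = 0.10: b/SE = 0.855; P(Z > 1.105) + P(Z < −2.815) = 0.135 + 0.002 = 13.7%.

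Relative to the 0.30 difference that section 10.2 pairs with 80 per arm, these shifts are 0.05/0.30 = 17% and 0.10/0.30 = 33%.

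The answer depends heavily on b. With the noncentral t at 80 per arm, assumed shifts of 0.1, 0.2 and 0.3 SD (0.074, 0.148 and 0.222 points) give 9.6%, 24.2% and 47.1%. These figures use the unadjusted SE. If baseline adjustment reduces the SE, as section 10.4.2 intends, the same shift weighs more.

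**The case against.** Asking people to use what they were assigned is ordinary delivery, and a polite reminder is not a requirement, so the letter does not flatly contradict section 7.1.2. The app arm openly includes a tutorial, technical support and a gift card or tablet, while control is described as close to usual care (7.1.1). The trial never claimed to match attention. This stands in part: it is a reason not to add a check-in call to controls, which would move that arm away from usual care. It does not justify different wording in two letters that could match at almost no cost. Nor does the protocol define encouragement as part of the intervention.

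A reader might infer that staff chase inactive users throughout. The text does not support this: the contact is tied to no activity at the start, its purpose is access and log-in, and no repeated reminders are described.

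A reader might also infer that controls get no prompt at all. That cannot be said. Weekly packets, if sent, would themselves be cues to read. In addition, the consent and disclosure text on expectations for participation was not available for review, and it may contain a reading expectation for everyone.

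Finally, naming the app in the control letter might be read as a contamination threat. It looks like a template carry-over. The enrolment email already names the app, the study library needs an invite code (15.6.7), and section 9.1 plans to check app data for control use. Contamination would in any case tend to shrink the contrast rather than inflate it.

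**Conclusion.** The concern holds as an avoidable difference between arms. The letters prompt reading unequally, this fits poorly with the self-led description and the stated contrast, and no planned analysis can separate the prompt from the app. The rise from 5% to about 7% to 14% rests on an assumed shift of 0.05 to 0.10 points, SD 0.74, 80 per arm and no true app effect. It shows what is at stake and does not estimate the bias.

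The documents do not show that prompting will produce a difference, or that a positive result would be due to it. The net imbalance in prompts is also unsettled until the control mailing schedule is reconciled. The point is worth acting on because the remedy is cheap and leaves the stated power calculation unchanged.

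**What to change.** - Put the same encouragement sentence in both letters and change only the medium, app or paper. Either the frequency wording or the permissive wording will serve, provided both arms get the same one.
- In the control letter, replace the reference to information in the app with 'these materials'.
- Reconcile the weekly packets in 11.1.4 (Step 7) with the single set in 15.7 and 15.7.4, so that the number of mailed prompts per arm is known.
- Keep the inactivity contact to the access and log-in check already described, record each one, and report study contacts by arm. Section 5.3 should acknowledge this contact alongside the two assessments.

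The cost is one IRB revision of the letters and a small amount of record keeping. If control reading rises, the contrast may shrink slightly, moving it closer to the app's own effect.

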## 15.7.2 INTERVENTION GROUP – GOGYUP READER QUICK START SHEET

This information sheet will be included with the welcome letter sent to study participants enrolled in the intervention (GogyUp Reader) group. This is meant as a supplement to the brief training provided by the research coordinator.

## How to Use GogyUp Reader

**Step 1**  
Download the **GogyUp Reader** from your mobile device's app store.

  
[Download on the App Store](#)  
[GET IT ON Google Play](#)

**~ OR ~**

[figure not shown]
Use **GogyUp Reader** on your computer with the Chrome or Edge browser:

  
<https://reader.gogyup.com>

**Step 2**  
Create your profile to save your progress.

**Step 3**  
Optional: Choose a **preferred language** if you want words translated.

**Step 4**  
Enter the **invite code** for the study:  
**ninr1**  
and click "Save profile"

[figure not shown]

**Features**

**A:** Touch any word to get help.

**B:** Hear the word, get a definition, translate it, or practice it.

**C:** Change how text is displayed.

**Need help? Call or Text: [contact]**

## 15.7.3 INTERVENTION GROUP - TABLET

If the participant requests to use a GogyUp-provided tablet, follow this procedure:

1. Connect with GogyUp Admin Assistant for tablet to be drop-shipped to participant.
2. Note tablet shipped date and serial number in participant's Study Database record.
3. Share estimated arrival date with participant via text and/or email:

#### 15.7.3.1 SHIPMENT NOTIFICATION SMS / EMAIL

*Hi, this is [your name] – GogyUp's Research Coordinator.*

[figure not shown]
*The tablet should arrive on [ ARRIVAL DATE AND TIME].*

*Please text / call / or email me when you receive it and have turned it on.*

*The tablet will be already configured to launch GogyUp – all you should need to do is turn it on! Of course, please contact me or contact me or GogyUp's technical support if you need help:*

eMail: [[contact]](mailto:[contact])

SMS / [contact]

---

#### 15.7.4 CONTROL GROUP – WELCOME LETTER

Use the following letter template to mail the hardcopy reading materials to study participants in the control group.

Street Address 1

Street Address 2

City, State Zip

[ DATE ]

Welcome to the study!

Here are your diabetes reading materials! Please feel free to review them over the next 12 weeks.

If you have questions about the study, contact our research coordinator:

- Phone / Text: [contact]
- eMail: [[contact]](mailto:[contact]).

You can also review study information here: [gogyup.com/study](http://gogyup.com/study)

Your follow-up assessment is scheduled for **{followupAssessmentDate}** at **{followupAssessmentTime}**. If you need to change it, please call the research coordinator: [contact]

Remember, the information in GogyUp Reader does not replace the information you receive from your doctor or clinic. **If you have questions about diabetes or your health, contact your doctor or clinic.**

Sincerely,  
The GogyUp Study Team

encl.

---

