### 7.1.2 ADMINISTRATION AND/OR DOSING

Given that this study involves assistive-reading technologies, administration and dosing are problematic concepts. However, to specify: participants will install GogyUp Reader app onto their devices (or devices supplied by GogyUp upon request) at baseline. A brief tutorial will be given by GogyUp staff trained in the protocol. The analog to “dosing” here is the degree to which participants might be expected to use the app or, if in the control group, review the paper documents. We are not requiring any particular level of app usage; our preliminary app usage data (GogyUp internal app data) have indicated consistent levels of self-directed app usage data in past applications and, to the degree intervention participants did not use the app, GogyUp would be able to see that in the app’s activity data (or lack thereof). Of course for the control group, activity data is not measurable.

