### 7.3 MEASURES TO MINIMIZE BIAS: RANDOMIZATION AND BLINDING

We will use a random allocation sequence from the National Cancer Institute's Clinical Trial Randomization Tool (<https://ctrandomization.cancer.gov/tool/>). Study staff will refer to the allocation sequence to determine allocation arm for each newly recruited participant.. As such, study staff not involved in analysis will not be blinded because they will provide initial access to the GogyUp Reader app. Lastly, using an encrypted Microsoft Excel file for which only study staff not involved in analysis will have the password, study staff will create and enter the study id and trial arm into two crosswalk files: the first, a crosswalk identifying study id number with study arm (for unblinding following blinded analysis), and a crosswalk file linking intervention-arm study identification numbers to a separate id number from GogyUp internal data (for assessments of adherence; see above). Study staff will then enter name, contact information, study id and baseline variables into REDCap. Investigators (Drs. [name], [name], and [name] and [name]) will be blinded to participants' status, only have access to the REDCap file prior to analysis, and indeed will not have contact with participants. To support interim analysis, all procedures above will be followed, but for participants recruited during the first three months, an additional study id variable (interim study id) and REDCap trial arm indicator (interim indicator) will be used— these will ensure that the interim analysis (see above) does not effectively unblind the full analysis. After *interim* analysis, study staff will use the encrypted file to inform the investigators which random study arm number indicated which study arm. After *final* analyses, study staff will provide the password for the encrypted crosswalk files to the investigators for unblinding. The criterion for unblinding will be that all participants have had a final follow-up visit and (masked/blinded) comparative analyses are complete. In the unlikely event of an *unplanned* unblinding/breaking of randomization indicators, because investigators have no contact with participants and this protocol will be registered publicly, instigators will simply report the unplanned breaking and reasons for it in all subsequent publications for transparency.

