### 9.1 ENDPOINT AND OTHER NON-SAFETY ASSESSMENTS

Assessments for this study will include eligibility assessment and initial contact for pre-screening, as well as baseline and follow-up measures. We will also extract internal app data for the study period to assess adherence in the intervention arm (and to ensure no contamination in the control arm).

To ensure a focus on equitable representation and on a sample reflective of our interest in low income (publicly or non-insured) patients, the study team and health system research support staff determined that initial contact with recruiting materials (see above) will be prioritized to individuals seen at primary care clinics in the health system that see the largest proportions of publicly insured or non-insured patients. Iterative mailings will continue to prioritize patients from these clinics as well as patients in historically excluded and underrepresented groups (e.g., Black or Indigenous patients) among those fitting initial eligibility criteria (see above). Health system staff will conduct pre-screening procedures including identifying a potential sample and sending recruitment mailings (see Recruitment Collateral below). To ensure candidates are fully opted-in, GogyUp and study staff will not have access to any potential participants until participants contact GogyUp by filling out an online intake form or calling, texting, or emailing the GogyUp Research Coordinator through a study-designated phone number and email address listed on the recruitment letter.

Once eligible participants are consented by the GogyUp Research Coordinator, enrollment and baseline assessments will take place within an expected two-week (maximum) timeframe. Baseline assessments will include study staff administration (remotely via phone or video call) of the validated Health Literacy Questionnaire subscales 9 and 2, "Understanding health information" and "Having sufficient information," as well as the secondary outcome of the PDSMS. At three months post-baseline, study staff will conduct follow-up administration of the same outcomes. Based on our theoretical mechanism of action (see above), health literacy is the primary set of

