##### 15.5.1.2 STEP 5A-1: CONTROL GROUP ASSIGNMENT

If participant is assigned to the control group (content only), state:

*Oh, great! You are assigned to what we're calling "the control group" – this is the group that will use standard, printed diabetes education materials. I will send them to you in the postal mail and they should arrive in 2 – 3 days.*

Note assignment in candidate's JotForm record and send materials in the postal mail.

---

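### Section 9.1 promises that app data will rule out control-arm contamination, but the planned linkage covers only the intervention arm and controls are never asked about app use; separately, the control letter carries an app sentence by mistake

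*Combined protocol and SAP*

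**What the plan says.** **The assurance.** Section 9.1 says internal app data for the study period will be extracted "to assess adherence in the intervention arm (and to ensure no contamination in the control arm".

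**The linkage.** Section 7.3 describes two crosswalk files. One ties study number to arm. The other is "a crosswalk file linking intervention-arm study identification numbers to a separate id number from GogyUp internal data", and its stated purpose is adherence assessment. Section 11.2.1 says app data are held by study id. The username instruction, that for the username "they should use their assigned" study number, appears in 15.6.7, which is intervention-arm onboarding. The same section notes that participants do not "have to use their real name" in the profile.

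**What controls are asked.** Sections 15.8 and 15.8.2 give controls the HLQ and PDSMS at follow-up. The user-experience items go to the intervention arm only.

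**Access to the app.** Section 5.1.2 describes an app for phones, tablets and ordinary browsers. Section 5.2 reports that people find and install it unaided, and the quick start sheet (15.7.2) points to the app stores and a web address. The study's own content sits in a walled library (11.1.4, step 7) opened by one shared invite code, ninr1.

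**The control condition and letter.** The assignment script (15.5.1.2) tells controls "this is the group that will use standard, printed diabetes education materials". Their welcome letter (15.7.4) nevertheless says "Remember, the information in GogyUp Reader does not replace the information you receive from your doctor or clinic". The same sentence stands in the intervention letter (15.7.1).

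**The concern.** The trial compares the app plus written materials with print alone. A control participant who uses the app moves the control mean towards the intervention mean and shrinks the contrast. Analysis is by intention to treat only (10.3), which is appropriate, but it means any crossover stays in the estimate. The reader then needs to know how much there was.

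Sections 5.3 and 7.4 plan to use app data to help explain why the arms did or did not differ. That works for low use in the intervention arm. It does not work for use in the control arm if nobody can tell which accounts belong to controls. A null result could then not be separated into an app that does not help and a control arm that also used it. This is a pilot meant to inform a larger trial, so an unmeasured crossover rate would carry into that planning. The unsupported assurance in 9.1 adds to the problem, because following the plan could lead the team to treat the absence of linked control accounts as evidence of no contamination.

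**Working it through.** **Step 1. Can the planned data show control use?** Two routes need separate treatment.

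- *Public app, no invite code.* The account carries no study number, because only intervention onboarding asks for one. It need not carry a real name. It is not in the crosswalk described in 7.3, and no questionnaire item asks about it. Under the plan as written, this use is invisible.
- *Study library, through the invite code.* The account would appear in the walled library as one more user. If its username is not an intervention-arm study number, it can be seen as an extra account, but nothing planned links it to a control participant.

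Neither route supports a claim to have ensured no contamination.

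**Step 2. Reproduce the plan's power figure.** Inputs from 10.2: Understanding subscale SD 0.74, difference 0.37 (SMD 0.5), 60 per arm, two-sample t-test. Two-sided alpha 0.05 is from 10.4.1.

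Standard error of the difference = 0.74 × √(2/60) = 0.1351.

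Power ≈ Φ(0.37/0.1351 − 1.96) = Φ(0.779) = 78.2% (noncentral t: 77.5%). The plan states 78%, so it reproduces. The target-enrolment figure does too: 80 per arm with difference 0.3 gives 72.7%, against 73% stated. Neither figure includes an allowance for contamination.

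**Step 3. Dilution, as an illustration.** Let c be the share of controls who use the app and gain its full effect, with the SD held at 0.74. The diluted difference is 0.37 × (1 − c). The documents give no value for c, so the rows below are assumptions.

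| Assumed c | Difference (from 0.37) | Power, 60 per arm | Power, 80 per arm (from 0.3) |
|---|---|---|---|
| 0% | 0.370 | 78.2% | 72.7% |
| 5% | 0.351 | 73.9% | 68.3% |
| 10% | 0.333 | 69.3% | 63.6% |
| 20% | 0.296 | 59.1% | 53.6% |

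The sample size needed to restore power rises by 1/(1 − c)²: 1.11 at 5%, 1.23 at 10%, 1.56 at 20%.

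**Step 4. Partial benefit.** If crossovers gain half the effect, 10% crossover gives 0.37 × (1 − 0.10 × 0.5) = 0.3515, which is the 5% row: 73.9% rather than 69.3%.

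**The case against.** *The protocol itself admits that control use cannot be measured.* A reader might infer this from 7.1.2: "Of course for the control group, activity data is not measurable". The context does not support it. That section has just defined the analogue of dosing for controls as reviewing the paper documents, so the sentence most naturally means that reading paper leaves no log. It neither contradicts 9.1 nor supports this point.

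*Control users could never be identified.* A reader might infer this too, and it goes too far. Study staff hold controls' contact details (15.5), a study number is assigned at enrolment (15.5.1.4), and the sponsor holds the app logs. The documents do not list the profile fields, and nothing says that the crosswalk in 7.3 is the only linkage allowed. What stands is that no method of detection is specified and that the linkage described cannot provide one.

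*The letter invites controls to use the app.* It does not. It gives no download link, no code and no suggestion to use it. The identical sentence in 15.7.1 points to template carry-over. The study web address it repeats was already in the recruitment letter, and candidates can read about GogyUp Reader before enrolling (11.1.4). The sentence is wrong text, but a weak cause of crossover.

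*Crossover may be rare or of little effect.* This is fair. The code is given in intervention materials only, and without it a control does not reach the study library. What benefit the public app alone would bring is unknown. The consent text is not in the copy reviewed, so whether controls are asked to avoid the app cannot be seen. This limits the likely size of the problem, but does not supply the missing check.

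**Conclusion.** The point holds as a gap between an assurance and its procedures. Section 9.1 promises to rule out control-arm contamination from app data. As planned, those data link only intervention-arm participants, and controls are asked nothing. Use of the public app by controls would go undetected, and use through the invite code would appear only as an unlinked account. The control letter's app sentence is a separate and minor text error.

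Confidence is high on both textual findings. The size is conditional: no crossover rate can be taken from the documents, so the loss of 4 to 19 percentage points of power (5% to 20% crossover at 60 per arm, from 78.2%) is illustrative. It assumes full benefit to crossovers and an unchanged SD. The plan's stated power figures are correct for zero contamination. It should not be concluded that contamination will occur or that the effect will be diluted, only that the plan could not tell. This should be fixed because the remedy is cheap and makes a null result easier to interpret.

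**What to change.** 1. In the control letter (15.7.4), replace the mention of GogyUp Reader with a reference to the enclosed reading materials. This is a one-sentence edit to participant material, subject to the usual IRB approval.
2. At follow-up, after the HLQ and PDSMS are recorded, ask control participants one yes/no question on whether they used GogyUp Reader during the study. The downside is that it draws attention to the app, so it must come after the outcomes. It is self-report, but also covers use without the invite code.
3. Have the study staff who are already unblinded list accounts opened with the ninr1 code whose username is not an intervention-arm study number. Where the profile fields allow, they should also match controls' contact details against app accounts. This is a data task for existing staff, and how far it goes depends on fields the documents do not list.
4. In 9.1, change the aim from ensuring no contamination to estimating it, name the sources in items 2 and 3, and report the estimated proportion of controls who used the app beside the ITT result. The ITT analysis itself does not change.

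If the sponsor prefers not to add detection, the minimum is to correct the letter and withdraw the assurance in 9.1.
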